8.2 Sample Size Determination

Primary analysis for Trial I. We power the study for each pairwise comparison. We will be comparing each arm against the others: oral valganciclovir vs placebo, topical ganciclovir 2% vs. placebo and oral valganciclovir vs. topical ganciclovir 2%. The power calculation was based on the primary outcome, log-transformed CMV viral load. We informed the calculation with viral loads from the pilot study, STACCATO. The STACCATO trial measured viral load at baseline and 7 days post-treatment. The standard deviation (SD) of log-transformed viral load 7 days post-treatment in STACCATO was 0.98. Since the primary analysis will adjust for baseline viral load, we used an estimate of the residual standard deviation, which is $SD_r = SD\sqrt{1 - r^2}$, where r is the correlation between the baseline measure and primary endpoint. In STACCATO, the correlation between baseline and post-treatment viral load was 0.50. Assuming a significance level of $0.05/2=0.025$ to account for multiple comparisons and an SD_r of 0.66 in \log_{10} viral load, we estimate that we will have 80% power to detect a difference of 0.50 in \log_{10} viral load (from 3.11 to 2.61) between arms with 35 study participants per arm (117 total allowing for approximately 10% loss to follow up). This calculation is based on the standard power formula for the T-test using an estimated residual standard deviation. While a global test of any difference between the three arms is possible, it is not clinically informative and the 2 pair-wise comparisons are of highest clinical interest. The proposed max-T procedure for P-value and simultaneous confidence interval estimation are a correct, valid approach for the two comparisons.²²

Primary analysis for Trial II. The primary outcome for Trial II is recurrence of inflammation (≥ 1 +anterior chamber cell) over 12 months. We calculated the effect size we would be able to observe with 80% power, a two-sided alpha of 0.05/2, and 28 participants per arm (105 total from Trial I with 20% loss to follow-up) based on a two-sample z-test for proportions. Assuming the risk of recurrence is 25% in the placebo group, we can detect a difference of 36 percentage points between the oral valganciclovir and the placebo groups. We acknowledge that having fewer recurrences in the placebo group compared to oral antiviral group may be contradictory to what one might think would typically occur with exposure to antivirals. However, it is well documented in the literature that long-term suppressive-level dosing of antiviral in an immunodeficient host or in an immunologically privileged organ (such as the eye) can create an environment permissive to the development of antiviral resistance.^{13-15,18,20}

For Specific Aim 3, we estimated the minimum detectable effect for the difference in prevalence of infections that have antiviral resistance mutations among recurrent infections in Trial II among patients who receive long-term antiviral prophylaxis compared with their infections at baseline. Aim 3 will focus on patients in the two active treatment arms in Trial II, because we would expect long-term use of topical and oral antivirals to lead to similar selection for antiviral resistance. From 117 participants enrolled, we conservatively assumed that 72% of patients would complete both Trial I and Trial II (n=84). We further assumed that 60% of patients will develop a recurrent infection over the monitoring period during the trials (Table 1)⁷. Participants who receive active treatment in Trial II (treatment regimens C+D) will contribute to the Aim 3 analysis (n=34). The analysis will be a paired analysis, comparing the proportion of recurrent infections with antiviral resistance mutations with that same proportion at baseline. *Please refer to the Statistical Analysis Plan (SAP) for further details.*

Randomization

For both trials, individuals will be randomized to the three arms in a 1:1:1 ratio. Randomization will be stratified by site. Stratified, block randomization will ensure that an approximately equal number of patients are randomized to each treatment arm by site. UCSF biostatistician will prepare the randomization and it will be implemented in REDCap.

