#### 3.3. Sample size

**Primary analysis for Trial I.** The power calculation was based on the primary outcome, base-10 logarithm-transformed CMV viral load. We informed the calculation with viral loads from our recently completed RCT, in which we measured viral load at baseline and 7 days post-treatment. The standard deviation (SD) of log-transformed viral load 7 days post-treatment in this RCT was 0.98. Since the primary analysis will adjust for baseline viral load, we used an estimate of the residual standard deviation, which is  $SD_r = SD\sqrt{1 - r^2}$ , where  $r$  is the correlation between the baseline measure and primary endpoint. In our recently completed RCT, the correlation between baseline and post-treatment viral load was 0.74. Assuming a significance level of 0.05/2=0.025 to account for multiple comparisons and an  $SD_r$  of 0.66 in  $\log_{10}$  viral load, we estimate that we will have 80% power to detect a difference of 0.50 in  $\log_{10}$  viral load (from

3.11 to 2.61) between arms with 35 study participants per arm (117 total allowing for approximately 10% loss to follow up). A reduction of 0.50 in  $\log_{10}$  viral load is equivalent to a  $10^{0.50} = 3.2$ -fold decrease in CMV viral load, which is small but clinically meaningful in the context of CMV antivirals that typically consider 10-fold reductions. This calculation is based on the standard power formula for the T-test using an estimated residual standard deviation.

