**Primary analysis for Trial II.** The primary outcome for Trial II is the proportion of participants experiencing CMV recurrence over 12 months. We acknowledge that hypothesizing fewer recurrences in the placebo group compared to the oral antiviral group is contradictory to what one might think would typically occur with exposure to antivirals. However, data from a previous observational study showed a one-year recurrence risk of 25.0% (3/12) among participants who did not receive antiviral treatment and 75.0% (9/12) in participants receiving systemic antiviral treatment (oral ganciclovir or valganciclovir), which is similar to the experience of other research. Additionally, it is well documented that long-term suppressive-level dosing of antiviral in an immunodeficient host or in an immunologically privileged organ (such as the eye) can create an environment permissive to the development of antiviral resistance. Given 28 participants per arm (105 total from Trial I with 20% loss to follow-up) and a recurrence risk of 25% in the placebo group, we can detect a difference of 40 percentage points between the oral valganciclovir and the placebo groups (from 25% to 65%), using a two-sample z-test for proportions with 80% power and a two-sided alpha of 0.05/2.

**For Specific Aim 3,** we estimated the minimum detectable effect for the difference in prevalence of infections that have antiviral resistance mutations among recurrent infections in Trial II among patients who receive long-term antiviral prophylaxis compared with their infections at baseline. Aim 3 will focus on patients in the two active treatment arms in Trial II, because we would expect long-term use of topical and oral antivirals to lead to similar selection for antiviral resistance. From 117 patients enrolled, we conservatively assumed that 72% of patients would complete both Trial I and Trial II (n=84). We further assumed that 60% of patients will develop a recurrent infection over the monitoring period during the trials (Table 1). Participants who receive active treatment in Trial II (treatment regimens C+D) will contribute to the Aim 3 analysis (n=34). The analysis will be a paired analysis, comparing the proportion of recurrent infections with antiviral resistance mutations with that same proportion at baseline.

Table 1. Anticipated participant enrollment, and follow-up by treatment patterns

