# 8. Revision history

Version	Date	Summary of Changes, Justification, and Timing vis-à-vis key trial events (enrollment completion, interim analyses, unmasking, etc)
1	2021-05-13	First version

2	2022-05-24	
 
Added pre-specified subgroup analyses by sex and by study site (section 6.4)
 
Added per-protocol analysis (section 6.4)
 
Added analyses of specific gene mutations (section 6.4)
 
Added details for interim analysis scenarios (section 3.5)
 

3	2025-01-15	
 
Updated sample sizes for Trial I and II based on results from prior trial and studies (section 3.3)
 
Changed primary aims for Trial II and updated the statistical methods accordingly (section 6.1, 6.2)
 
Removed per-protocol analysis because all participants adhered to their assigned treatment; removed subgroup analysis by site because there was one site with only a few participants, which would not provide sufficient statistical power for a meaningful analysis (section 6.4)
 

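### Protocol 8.2: the residual SD for Trial I and the detectable difference for Trial II do not follow from the Protocol's own inputs, and both calculations disagree with SAP 3.3

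*Protocol*

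**What the plan says.** **Trial I.** Protocol 8.2 states: "The standard deviation (SD) of log-transformed viral load 7 days post-treatment in STACCATO was 0.98". It defines the residual SD as SD × √(1 − r²), where r is the correlation between the baseline and day-7 values, and continues: "In STACCATO, the correlation between baseline and post-treatment viral load was 0.50". It then assumes "an SD_r of 0.66 in" log10 viral load and concludes that 35 evaluable participants per arm (117 enrolled, about 10% loss) give 80% power for a difference of 0.50 log10 at a significance level of 0.025.

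SAP 3.3 has the same SD, formula, residual SD, difference, sample size, significance level and power. It differs on one input: "the correlation between baseline and post-treatment viral load was 0.74".

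**Trial II.** Protocol 8.2 assumes 80% power, two-sided alpha of 0.05/2, a 25% recurrence risk on placebo and "28 participants per arm (105 total from Trial I with 20% loss to follow-up) based on a two-sample z-test for proportions". Its result is: "we can detect a difference of 36 percentage points between the oral valganciclovir and the placebo groups". SAP 3.3 uses the same risk, power, alpha, number per arm and test, and reports 40 points, from 25% to 65%.

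The entry for version 3 in the SAP's revision history (section 8) reads: "Updated sample sizes for Trial I and II based on results from prior trial and studies".

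**The concern.** In each trial the two documents run one calculation and disagree on a number in it. In Trial I they report different observed correlations and arrive at the same residual SD, so at most one correlation can be right. In Trial II they start from identical inputs and report different detectable differences, so at most one result can be right.

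These paragraphs carry the power statements for both primary endpoints. A reader of the Protocol cannot tell whether Trial I has adequate power or is well short of it, and for Trial II is told of a smaller detectable effect than the design supports. The discrepancy also reaches the interim analysis. Protocol 8.3.1 and SAP 3.5 base the futility guideline on conditional power under the assumed design effect, and for Trial II the two documents supply two candidates for it, 36 and 40 points.

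**Working it through.** **Trial I inputs** (Protocol 8.2): SD 0.98; r 0.50 (SAP 3.3: 0.74); difference 0.50 log10; 35 per arm; alpha 0.025, two-sided according to SAP 4.1; t-test power formula with the residual SD.

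*Step 1, from r to residual SD.*
- Protocol: 0.98 × √(1 − 0.50²) = 0.98 × 0.866 = 0.849, not 0.66.
- SAP: 0.98 × √(1 − 0.74²) = 0.98 × 0.673 = 0.659, which rounds to 0.66.
- Solving backwards: r = √(1 − (0.66/0.98)²) = 0.739.
- Rounding does not close the gap: r between 0.495 and 0.505 gives 0.852 to 0.846. Reading 0.50 as r² gives 0.98 × √0.50 = 0.693, which also misses.

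*Step 2, from residual SD to power.* Taking 0.66 as given, the noncentrality is 0.50 / (0.66 × √(2/35)) = 3.17 on 68 degrees of freedom, and power is 80.8%. Enrolment is 35/0.9 = 38.9, so 39 per arm and 117 in total. The plan's power and sample size therefore reproduce. Only step 1 fails.

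*Step 3, how much depends on r* (35 per arm, difference 0.50 log10, two-sided alpha 0.025):

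| r | Residual SD | Power |
|---|---|---|
| 0.74 | 0.659 | 80.9% |
| 0.70 | 0.700 | about 75.5% |
| 0.60 | 0.784 | 64.7% |
| 0.50 | 0.849 | 57.0% |

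At r = 0.50 the difference detectable with 80% power is 0.64 log10, and 80% power for 0.50 log10 would need 57 evaluable per arm. At 10% loss that is 57 × 3 / 0.9 = 190 enrolled, or 192 if each arm is rounded up to 64.

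**Trial II inputs** (Protocol 8.2 and SAP 3.3): 28 per arm (105/3 × 0.8); placebo risk 0.25; two-sided alpha 0.025, z = 2.241; power 80%; two-sample z-test for proportions.

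For the pooled form, with p̄ the mean of p₁ and p₂, power = Φ{ [ |p₂ − p₁|√n − z√(2p̄(1 − p̄)) ] / √(p₁(1 − p₁) + p₂(1 − p₂)) }.

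- SAP, 0.25 against 0.65: (2.117 − 2.241 × 0.704) / 0.644 = 0.838, power 79.9%. The SAP's 40 points reproduces.
- Protocol, 0.25 against 0.61: (1.905 − 2.241 × 0.700) / 0.652 = 0.515, power 69.7%. The Protocol's 36 points does not.

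Neither document says which form of the z-test was used, so all three are shown:

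| Form | Power for 36 points, 28 per arm | Difference detectable with 80% power | n per arm needed for 36 points |
|---|---|---|---|
| Pooled | 69.7% | 40.0 | 35 |
| Arcsine | 70.8% | 39.8 | 35 |
| Unpooled | 75.2% | 37.8 | 32 |

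None gives 36. With the pooled form, 36 appears only if a stated input is changed: alpha 0.05 instead of 0.025 at 28 per arm (detectable difference 36.3), or 35 per arm with no loss at alpha 0.025 (35.8). The documents do not say whether either was used.

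**The case against.** The strongest reply is that no design quantity has been shown to be wrong. In Trial I, the residual SD, difference, number per arm and total agree across both documents and reproduce with r = 0.74. For r = 0.50 to be the true value, the 0.66 in both documents would have to be wrong and the SAP's 0.74 would have to match it by coincidence. In Trial II, the 28 per arm is inherited from Trial I and not derived from the detectable difference, so changing 36 to 40 alters neither enrolment nor analysis. The Protocol refers readers to the SAP for details. The 36 may be a figure before losses, since the Trial II schema shows 35 per arm. The observational data that motivate the Trial II hypothesis in SAP 3.3 show 25% against 75%, and power for that 50-point gap at 28 per arm is about 95% to 98%.

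Much of this stands. The r = 0.50 case is a contingency and not the likely state of affairs, and the enrolment of about 190 is not being asked for. But referring to the SAP for details does not withdraw figures that the current Protocol states as its own. The text attaches 36 to 28 per arm after loss, so a pre-loss origin would confirm the error. The 50-point gap comes from 12 patients per group and does not make the 36-point claim true. The objection also shows that arcsine (39.8) rounds to 40 as well, so the form of the z-test is for the sponsor to state.

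**Conclusion.** Both discrepancies hold. Protocol 8.2's SD of 0.98 and r of 0.50 give a residual SD of 0.85, not 0.66. Its Trial II inputs give a detectable difference of about 40 points (37.8 in the most favourable form), not 36, and the 80% power claimed for 36 points is 70% to 75%. Both SAP 3.3 figures reproduce from the SAP's own inputs.

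For Trial I the likely explanation is a wrong r in the Protocol, in which case the planned 80% power and 117 participants stand. That rests on the agreement between the documents and on the assumption that the Protocol's pilot study and the SAP's recently completed trial are the same study, as the shared SD suggests. The underlying data are not in the documents, so r has to be confirmed; if it were 0.50, power would be 57%. For Trial II the conclusion does not depend on which of the three forms of the z-test is taken. The figures must be corrected, because they are the stated power basis for both primary endpoints.

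**What to change.** 1. Check r against the completed trial's data. If it is 0.74, replace 0.50 by 0.74 in Protocol 8.2; nothing else in the Trial I calculation changes. If it is 0.50, restate the residual SD as 0.85, the power as 57% and the detectable difference as 0.64 log10 in both documents, and say whether 117 participants is still accepted.
2. In Protocol 8.2, replace 36 by 40 percentage points (25% to 65%), in line with SAP 3.3, and state in both documents which form of the z-test was used. The pooled form reproduces 40 with 79.9% power; arcsine also rounds to 40.
3. Use the corrected Trial II difference as the single assumed effect for the futility calculation.

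If r is 0.74, the cost is two corrected numbers in the Protocol and a less favourable, but correct, statement for Trial II, with no extra participants. If r is 0.50, the sponsor must either accept a stated power of 57% at the present size or enrol about 190 to keep 80%.

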8.3 Statistical Analyses

1a. The Aim 1 primary outcome **viral load after 7 days of treatment** will use the results from quantitative PCR at 7 days of treatment or placebo therapy (day 7 of trial). All quantitative PCR viral loads will undergo log transformation, with units converting from IU/mL to log IU/mL.

1b. **Clinical inactivity of inflammation:** At each study visit patients will be clinically examined, and a study ophthalmologist will make a clinical determination as to whether the patient's inflammation is considered inactive (defined as $\leq 0.5+$ anterior chamber cell). The proportion of participants that achieve clinically inactive inflammation by day 7 and 21 will be compared by arm. Patients will also be administered a questionnaire querying when they felt symptomatic improvement in their condition. This analysis will be viewed as hypothesis generating and will be treated as supplementary and in addition to the main finding.

2a. **Recurrence of inflammation over 12 months:** After achieving clinical quiescence, participants will be offered enrollment into Trial II where they would be re-randomized to long-term suppressive treatment to study the effect on recurrence of inflammation (defined as $\geq 1+$ anterior chamber cell). Each participant will be assessed for recurrence at each visit. Alternatively, if participants experience symptoms of a flare up, they will be instructed to contact the local site clinical coordinator or study ophthalmologist for an examination within 3 days. If recurrence of inflammation occurs, aqueous chamber fluid will be collected (an anterior chamber paracentesis will be performed) from participant to quantify viral load.

3a. **Prevalence of mutations conferring antiviral resistance:** The analysis population will include individuals enrolled in both Trials I and II who are randomized to receive oral or topical antivirals in Trial II and experience a recurrent infection. Among patients that experience a

recurrent infection (anticipated n=34, see Sample Size section 3.3 in SAP), we will compare the proportion of infections with antiviral mutations upon recurrence with the proportion with antiviral mutations at baseline.

Interim Analysis

The interim analysis for each trial should be conducted after one-third and before one-half of the patients have been enrolled; ideally when there are 15 patients per arm.

8.3.1 SAFETY ANALYSES

Interim reports for the DSMC will be prepared by the central Proctor site.

The Data and Safety Monitoring Committee will meet to review the interim efficacy data when primary outcome data is available on one third of the study subjects. The DSMC will make one of the following recommendations:

- Continue the study without modifications
- Continue the study with modifications
- Terminate enrollment or treatment in the study because of safety concerns
- Terminate enrollment or treatment in the trial because of futility

The DSMC will determine the database closure dates for each report in advance; archival copies of the (a) main database, and (b) study analysis file as they exist at the time of each report will be maintained. All reports will be sent using secure email to the members of the DSMC two weeks prior to each meeting.

The DSMC will make decisions with the benefit of pre-specified decision guidelines. These guidelines will be agreed upon at the initial meeting, and are expected to include (a) safety, (b) efficacy, (c) futility, (d) clinical importance, or (e) validity.

Efficacy. Unmasked interim analyses will be conducted to determine whether or not sufficient evidence has accumulated to justify stopping the trial because one treatment is clearly superior (and therefore should be extended to all future cases). The guidelines for efficacy will use group sequential boundaries for judging the statistical significance of the primary outcome measure. The Lan and DeMets²³ flexible alpha spending approach with a power function is suggested, with $\alpha^*(t^*) = \alpha (t^*)^\theta$, where $\theta = 3.561$ chosen so that the two-sided *P*-value to stop the trial for efficacy is 0.001.

Harm. Stopping for harm will be done at the judgment of the DSMC. Several endpoints will be examined, including adverse events, and especially abnormal lab results meeting the designated threshold of a serious adverse event.

All subjects who provide informed consent will be accounted for in this study. We will present the number lost to follow-up and the number of protocol deviations by arm. The proportion of

subjects reporting adverse events and serious adverse events will be reported by arm to the DSMC and will be compared using a Fisher's Exact Test.

Futility. Early discontinuation due to the unlikelihood of significant findings conditional on interim results may be considered, based on the original sample size considerations. For evaluating futility, we propose to use a simulation-based approach²⁴ that estimates conditional power under the assumed design effect for the remainder of participants and under the current trend observed at the interim analysis. We propose that the DSMC consider discontinuation for futility if the conditional power to detect a difference in viral load in Trial I and recurrence in trial II drops below 20% at the interim analysis under the assumed design effect for the remainder of participants yet to be enrolled.

Population for Analyses

Individual level missing data (due to loss to follow-up or dropouts) is expected. Complete analysis will be reported. Missing values will be tabulated by treatment arm, and study site. Sensitivity analysis assigning outcomes to the missing values will be reported. Additionally, analyses will be reported in which we adjust for any baseline covariate known to be a predictor of missing outcome data. **Please refer to the SAP for further details regarding analyses.**

9 SUPPORTING DOCUMENTATION AND OPERATIONAL CONSIDERATIONS

9.1 Regulatory, Ethical, and Study Oversight Considerations

9.1.1 INFORMED CONSENT PROCESS

9.1.1.1 Consent/assent and Other Informational Documents Provided to participants

Consent forms describing in detail the study intervention, study procedures, and risks are given to the participant and written documentation of informed consent is required prior to starting study procedures. Consent forms will be given to the participant in their native language.

9.1.1.2 Consent Procedures and Documentation

Informed consent is a process that is initiated prior to the individual's agreeing to participate in the study and continues throughout the individual's study participation. Consent forms will be Institutional Review Board (IRB)-approved and the participant will be asked to read and review the document. The investigator will explain the research study to the participant and answer any questions that may arise. A verbal explanation will be provided in terms suited to the participant's comprehension of the purposes, procedures, and potential risks of the study and of their rights as research participants. Participants will have the opportunity to carefully review the written consent form and ask questions prior to signing. The participants should have the opportunity to discuss the study with their family or surrogates or think about it prior to agreeing to participate. The participant will sign the informed consent document prior to any procedures being done specifically for the study. Participants must be informed that participation is voluntary and that they may withdraw from the study at any time, without prejudice. A copy of the informed consent document will be given to the participants for their records. The informed consent process will be conducted and documented in the source document (including the date), and the form signed, before the participant undergoes any study-specific procedures. The rights and welfare of the participants will be protected by emphasizing to them that the quality of their medical care will not be adversely affected if they decline to participate in this study.

